Optional biomarker mRNA ^t				X													X ^s		
Crohn's Disease Activity Index (CDAI)		X		X	X	X	X	X	X ^y	X	X ^y	X	X ^y	X	X ^y	X ^y	X	X	
Start Corticosteroid Taper ^t						X													
Monitor Adverse Events ^u	X	X	X	X	X	X	X	X	X ^y	X	X ^y	X	X ^y	X	X ^y	X ^y	X	X	X
Study Drug Dispensing/ Administration ^v				X	X	X	X	X	X ^w	X	X ^w	X	X ^w	X	X ^w	X ^w	X	X ^x	
Inflammatory Bowel disease Questionnaire (IBDQ)				X		X											X		

- Day - 21 and Day -7 visits are required for subjects who initiate TB prophylaxis during the screening period. If a subject does not initiate TB prophylaxis, these visits are not required.
- The Baseline (Week 0) visit date will serve as the reference for all subsequent visits. A ± 3-day window is permitted around scheduled study visits.
- Subjects will be contacted 70 days following study drug discontinuation for an assessment of any new or ongoing AEs, except those subjects who initiate adalimumab therapy not supplied in the context of the clinical trial after the end of study participation.
- Update inclusion/exclusion, prior and concomitant therapy, and medical/surgical history information to assure subject eligibility.
- Height will be measured at Screening only.

Table 1. Study Activities (Continued)

- f. Diary should be brought back to the site at every visit.
- g. Physical examination performed at Screening, Week 4, Week 8, and Week 26/Premature Discontinuation Visits are full physical examinations and those performed at all other visits are symptom-based and TB symptoms are discussed.

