Blood samples for antinuclear antibody (ANA) will be obtained per [Table 1](#). Anti-double-stranded DNA (anti-dsDNA) assessments will be performed if ANA is positive.

In the event that subject develops lupus-like symptoms during the study, an additional ANA sample will be obtained.

hs-CRP

Blood samples for hs-CRP will be obtained per [Table 1](#). The site will receive the notification from the central laboratory for the Screening Period. Results obtained during the Day -7 Screening visit (for a subject who started TB prophylaxis) will be used for entry criteria.

The hs-CRP results from Week 2 through Week 8 will remain blinded to Investigator, study site personnel and the subject. The AbbVie safety team will not be blinded to these results. Since investigators are blinded to hs-CRP, the SDP will notify the investigator of an elevated hs-CRP result (> 100 mg/L) and request follow-up.

Blood draws should be performed after all clinical assessments and questionnaires (including CDAI), vital sign determinations are obtained and before study drug administration during a visit.

Fecal Calprotectin

Fecal calprotectin will be performed for all subjects as indicated in [Table 1](#) and collection should be performed before study drug administration during a visit as much as possible.

If subjects are unable to provide a sample at the site visit, they will be sent home with a stool sample collection supplies and instructions to assist the subjects with the collection procedures.

The fecal calprotectin results will remain blinded to Investigator, study site personnel and the subject up to and including Week 8.

The central laboratory will be utilized to process and provide results for these laboratory tests.

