4.2 Design Diagram

This is a Phase 3, randomized, double-blind, placebo controlled, multicenter study of adalimumab in anti-TNF naïve Chinese subjects with moderately to severely active CD ($220 \leq \text{CDAI} \leq 450$) and elevated hs-CRP ($\geq 3 \text{ mg/L}$). The study consists of an 8-week DB period followed by an OL period of 18 weeks. Subjects will be randomized in a 1:1 ratio to receive adalimumab or placebo at Baseline. Subjects randomized to adalimumab at Week 0 will receive blinded adalimumab 160 mg at Week 0, 80 mg at Week 2, and 40 mg at Week 4 and Week 6. Subjects randomized to placebo at Week 0 will receive blinded placebo at Week 0 and Week 2, then will receive blinded adalimumab 160 mg at Week 4 and 80 mg at Week 6. At Week 8, all subjects will enroll in an 18-week OL period to receive adalimumab 40 mg every other week (eow). No drug will be administered at the final study visit.

The study was designed to enroll approximately 200 subjects to meet scientific and regulatory objectives without enrolling an undue number of subjects in alignment with ethical considerations.

[figure not shown]
The study duration will be up to 39 weeks, and will include a screening period of up to 35 days, an 8-week double blind treatment period, an 18-week OL period and a 70-day follow-up period. All subjects will have a follow-up phone call approximately 70 days after the last administration of study drug to obtain information on any new or ongoing AEs. The 70-day follow-up phone call will not be required for any subject who initiates adalimumab therapy not supplied in the context of Study M14-233 after the end of study participation.

At or after Week 12, any subject who experiences inadequate response may increase dose to OL adalimumab 80 mg eow. If the subject has received OL 80 mg eow therapy and continues to demonstrate inadequate response, he or she should be withdrawn from the study per PI discretion.

Subjects may discontinue adalimumab treatment at any time during study participation. Subjects who end study participation early will have a Premature Discontinuation Visit.

A schematic of the study design is shown in [Figure 1](#).

Figure 1. Study Design

The study activities are presented in [Table 1](#).

Table 1. Study Activities

Activity	Screening (35 Days)	Day -21 ^a	Day -7 ^a	Baseline (Wk 0) ^b	Wk 2	Wk 4	Wk 6	Wk 8	Wk 10	Wk 12	Wk 14	Wk 16	Wk 18	Wk 20	Wk 22	Wk 24	Wk 26/ Premature Discontinuation	Unscheduled Visit	70-Day Follow-Up Call ^c

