Since subjects do not always adhere to the study visit schedule, the following rules will be applied to assign actual visits to protocol-specified visits including early termination visits. For each study visit mentioned in the protocol, a nominal or target day will be selected to represent the corresponding visit along with a window around the target day. Windows will be selected in a non-overlapping fashion so that a date collected on the CRF does not correspond to multiple visit windows. Moreover, windows will not discard any post-baseline measurement recorded on the CRF. If a subject had two or more actual visits in one visit window, the visit closest to the target will be used as the study visit for that window. If two visits are equidistant from the target, then the later visit will be used for reporting. For efficacy related analyses, if multiple measurements for a particular parameter are collected on the same day for the same subject, the average of those measurements will be used. For safety related analyses, if multiple measurements are made for a particular laboratory or vital sign parameter on the same day for the same subject, the average of the values will be used in the analyses. For summaries and listings of shift from baseline and potentially clinically significant values all values will be considered in the analyses.

Table 2. Visit Windows for Analysis of CDAI and Vital Sign

Scheduled Week	Nominal Day	Time Window (Rx Day A Range)
Week 0 DB	1 ^a	≤ 1
Week 2 DB	15	2 – 22
Week 4 DB	29	23 – 36
Week 6 DB	43	37 – 50
Week 8 DB	57	51 – 64 ^b
Week 10 OL	71	65 ^c – 78
Week 12 OL	85	79 – 92
Week 14 OL	99	93 – 106
Week 16 OL	113	107 – 120
Week 18 OL	127	121 – 134
Week 20 OL	141	135 – 148
Week 22 OL	155	149 – 162
Week 24 OL	169	163 – 176
Week 26 OL	183	177 – 190

Rx Day A = date of visit – date of first study drug injection in double-blind treatment period + 1

- a. Date of first study drug injection in double-blind treatment period.
- b. For Week 8 DB, visit window was from Rx Day 51 to Rx Day 64 or the date of the first injection in OL period (if applicable), whichever comes first.
- c. For Week 10 OL, visit window was from Rx Day 65 or the date of the first injection in OL period + 1 (if applicable), whichever comes first, to Rx Day 78.

Table 3. Visit Windows for Analysis of hs-CRP, Chemistry and Hematology

Scheduled Week	Nominal Day	Time Window (Rx Day A Range)
Week 0 DB	1 ^a	≤ 1
Week 2 DB	15	2 – 22
Week 4 DB	29	23 – 36
Week 6 DB	43	37 – 50

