Week 8 DB	57	51 – 71 ^b
Week 12 OL	85	72 ^c – 99
Week 16 OL	113	100 – 127
Week 20 OL	141	128 – 162
Week 26 OL	183	163 – 190

Rx Day A = date of visit – date of first study drug injection in double-blind treatment period + 1

- a. Date of first study drug injection in double-blind treatment period.
- b. For Week 8 DB, visit window was from Rx Day 51 to Rx Day 71 or the date of the first injection in OL period (if applicable), whichever comes first.
- c. For Week 12 OL, visit window was from Rx Day 72 or the date of the first injection in OL period + 1 (if applicable), whichever comes first, to Rx Day 99.

Table 4. Visit Windows for Analysis of Urinalysis

Scheduled Week	Nominal Day	Time Window (Rx Day A Range)
Week 0 DB	1 ^a	≤ 1
Week 4 DB	29	2 – 43
Week 8 DB	57	44 – 71 ^b
Week 12 OL	85	72 ^c – 112
Week 20 OL	141	113 – 161
Week 26 OL	183	162 – 190

Rx Day A = date of visit – date of first study drug injection in double-blind treatment period + 1

- a. Date of first study drug injection in double-blind treatment period.
- b. For Week 8 DB, visit window was from Rx Day 37 to Rx Day 71 or the date of the first injection in OL period (if applicable), whichever comes first.
- c. For Week 12 OL, visit window was from Rx Day 72 or the date of the first injection in OL period + 1 (if applicable), whichever comes first, to Rx Day 112.

Table 5. Visit Windows for Analysis of Fecal Calprotectin and IBDQ

Scheduled Week	Nominal Day	Time Window (Rx Day A Range)
Week 0 DB	1 ^a	≤ 1
Week 4 DB	29	2 – 43
Week 8 DB	57	44 – 71 ^b
Week 26 OL	183	72 ^c – 190

Rx Day A = date of visit – date of first study drug injection in double-blind treatment period + 1

- a. Date of first study drug injection in double-blind treatment period.
- b. Rx Day 71 or the date of the first injection in OL period (if applicable), whichever comes first.
- c. For Week 26 OL, visit window was from Rx Day 72 or the date of the first injection in OL period + 1 (if applicable), whichever comes first, to Rx Day 190.

Vital signs and laboratory measurements will also be presented on the Any Adalimumab set using the visit windows in the following tables.

Table 6. Visit Windows for Analysis of CDAI and Vital Sign (Any Adalimumab)

Visit Week	Nominal Day	Time Window (Rx Day B Range)
Week 0	1 ^a	≤ 1
Week 2	15	2 – 22
Week 4	29	23 – 36
Week 6	43	37 – 50
Week 8	57	51 – 64
Week 10	71	65 – 78
Week 12	85	79 – 92
Week 14	99	93 – 106
Week 16	113	107 – 120
Week 18	127	121 – 134
Week 20	141	135 – 148

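### The Week 4 analysis windows are not cut at the Week 4 injection, so a value taken after a placebo subject's first adalimumab dose can be scored as that subject's Week 4 result; the likely effect on the primary endpoint is small.

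*SAP*

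**What the plan says.** Under the design (SAP 4.2), subjects randomized to placebo get placebo at Weeks 0 and 2, "then will receive blinded adalimumab 160 mg at Week 4 and 80 mg at Week 6". The primary comparison at Week 4 is therefore meant to use the last assessment before the control arm becomes an active arm.

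SAP 6.0 maps actual visits, including early termination visits, to scheduled weeks by days counted from the first injection. The target for Week 4 is Day 29. The windows are Days 23-36 for CDAI (Table 2) and hs-CRP (Table 3), and Days 2-43 for fecal calprotectin and IBDQ (Table 5). No Week 4 row has a footnote tying it to the Week 4 injection. Within a window, "the visit closest to the target will be used as the study visit for that window". On ties, "If two visits are equidistant from the target, then the later visit will be used for reporting". The SAP adds that "windows will not discard any post-baseline measurement recorded on the CRF". SAP 10.2 sets no on-or-before-dose condition for the primary endpoint.

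The SAP does use treatment-related cuts elsewhere:
- The Week 8 rows are cut at the first open-label dose. Table 2, for example, reads: "For Week 8 DB, visit window was from Rx Day 51 to Rx Day 64 or the date of the first injection in OL period".
- Treatment-emergent adverse events in the placebo-controlled period stop at the Week 4 dose (SAP 11.2.1). SAP 12.1 explains that placebo subjects then start adalimumab induction.
- By contrast, the final observation of the 4-week placebo-controlled period runs to the Week 6 dose for subjects who continue (SAP 6.0).

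On visit timing, the protocol states: "A ± 3-day window is permitted around scheduled study visits". On stool, it asks for collection before dosing as far as possible, then allows: "If subjects are unable to provide a sample at the site visit, they will be sent home with a stool sample collection supplies".

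**The concern.** The Week 4 contrast is adalimumab against placebo. A value taken from a placebo subject after 160 mg of adalimumab does not belong to that contrast, yet the selection rule looks only at distance from Day 29 and favours the later record on a tie. The rule can act in two ways. It can displace a valid pre-dose value, or it can supply a value where the pre-dose one is missing and non-responder imputation (NRI) should apply. The rule covers the primary endpoint, the Week 4 key secondary endpoints, and the efficacy analyses over time for Weeks 0 to 4. The adverse-event analysis already stops at the Week 4 dose, so efficacy and safety would describe different placebo-controlled periods.

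**Working it through.** **1. The plan's own figure.** Inputs (SAP 4.3): 24% against 47%, 100 per arm, two-sided Fisher's exact test at 0.05, stated power 90%. Summing both binomial distributions over all tables that Fisher's test rejects gives 90.7%. The stated figure is reproduced.

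**2. Which days can enter.** The ±3-day allowance puts the Week 4 visit and injection on Days 26-32. Let v be the visit and injection day, and d a later measurement day. A post-dose value replaces an existing pre-dose value when d > v and |d − 29| ≤ |v − 29|, equality being settled by the tie rule.

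| v | Post-dose days left in Days 23-36 | Days d that replace the pre-dose value | Post-dose days left in Days 2-43 |
|---|---|---|---|
| 26 | 10 | 27-32 | 17 |
| 27 | 9 | 28-31 | 16 |
| 28 | 8 | 29-30 | 15 |
| 29 | 7 | none | 14 |
| 30 | 6 | none | 13 |
| 31 | 5 | none | 12 |
| 32 | 4 | none | 11 |

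The tie rule decides 26 v 32, 27 v 31 and 28 v 30. For example, a visit on Day 26 is 3 days from target and an unscheduled CDAI on Day 31 is 2 days from it, so Day 31 is used. For v = 29 to 32, a post-dose value is used only if there is no pre-dose value, for instance with fewer than 4 diary days.

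**3. Where such values come from.** Protocol Table 1 schedules CDAI and hs-CRP at unscheduled and premature discontinuation visits. An on-time Week 6 visit falls on Days 40-46, outside Days 23-36, so it cannot be used as Week 4 CDAI or hs-CRP. For stool, the main route is home collection after the visit.

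**4. What a post-dose CDAI contains.** SAP 6.0 sums up to 7 diary days preceding the visit. Protocol 5.3.1.1 takes hematocrit from the preceding visit's laboratory work.
- Dose Day 28, extra visit Day 30: diary Days 23-29, that is 5 pre-dose days, the dose day and 1 post-dose day.
- Dose Day 26, extra visit Day 31: diary Days 24-30, that is 2 pre-dose days, the dose day and 4 post-dose days.

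The hematocrit in both cases is from the Week 4 draw, which is to precede dosing whenever possible. These values mix placebo and early adalimumab time.

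**5. Size for the primary endpoint.** The documents give no frequency. Assume a share f of placebo subjects is scored on a post-dose value and remits at 47% instead of 24%. The placebo rate is then 24 + 23f.

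| f | Placebo rate | Difference (points) | Fisher power |
|---|---|---|---|
| 0 | 24.0% | 23.0 | 90.7% |
| 1% | 24.23% | 22.77 | 90.1% |
| 2% | 24.46% | 22.54 | 89.4% |
| 5% | 25.15% | 21.85 | 87.2% |
| 10% | 26.3% | 20.7 | 82.9% |

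Given the conditions in steps 2 and 3, the 1-2% rows are the more plausible ones. Because of step 4, applying the full 47% to these subjects is generous to the concern.

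**The case against.** The strongest case against acting is that this is a drafting gap with little practical effect. Protocol Table 1 and the laboratory section place assessments before dosing where possible. The primary-endpoint route needs an extra, discontinuation or off-schedule visit by Day 36, together with a Week 4 visit on Days 26-28 or a missing pre-dose CDAI. The resulting CDAI is only partly post-drug. All of this stands, and it limits the size of the problem. It does not make the rule right, because nothing in the SAP prevents the wrong record from being chosen.

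A reader might infer three stronger points that the documents do not support:
- **That the gap necessarily biases the difference towards zero.** Drug effect alone would. But unscheduled and discontinuation visits may occur because a subject is worse, and such a value could turn a placebo remitter into a non-remitter.
- **That the Week 8 cut shows the SAP saw this problem one visit late.** At Week 8 both arms are already on adalimumab; that cut separates the double-blind and open-label periods. The relevant precedent is the Week 4 adverse-event cut.
- **That a sizeable share of Week 4 stool samples is contaminated.** No such share is given. The 14 days between Day 29 and Day 43 is a window limit, not an expected delay. IBDQ has little exposure: neither it nor stool appears in the protocol's unscheduled-visit column, and questionnaires precede the blood draw, which precedes dosing where possible.

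The objection also bears on the remedy for Table 5. Week 4 is the first scheduled post-baseline calprotectin, and the SAP bars carrying baseline forward, so last observation carried forward (LOCF) would normally have nothing to use. For the calprotectin composite, NRI would fail late samples in both arms. If a share f is late independently of outcome, both rates are multiplied by (1 − f), and so is their difference. A hard cut could therefore lose as much as it protects. That stands, and the fix for Table 5 differs for this reason.

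**Conclusion.** The gap is real: under the Week 4 rows of Tables 2, 3 and 5, a value taken after a placebo subject's first adalimumab dose can be used as the Week 4 placebo result, including for the primary endpoint. That conclusion rests on the text alone. The size rests on assumption. For the primary endpoint few subjects are likely to be affected, and at 1-2% the loss of power is about 0.6 to 1.3 percentage points (90.7% to 90.1% or 89.4%). The net direction is uncertain. The documents do not support calling the primary analysis materially biased. The point merits correction before database lock because the rule can give a wrong primary value and the CDAI and hs-CRP repair is nearly free. For calprotectin the window is wider and home collection gives a plausible route, but the extent is unknown.

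**What to change.** **Tables 2 and 3.** Add a footnote ending the Week 4 window at the earlier of Day 36 or the Week 4 injection date (if there was one), with the Week 6 window starting the next day. Apply it to both arms. Where no such value exists, use NRI for binary endpoints.

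**Final observation.** Align the definition for the 4-week placebo-controlled period, now running to the Week 6 dose, with the Week 4 cut used for adverse events.

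**Table 5.** Do not impose a hard cut. Prefer any value on or before the Week 4 injection over a later one. Keep the Week 8 window start at Day 44, because starting it the day after the Week 4 injection could label an early sample as Week 8. Flag stool samples taken after the injection, and add a sensitivity analysis of the Week 4 calprotectin endpoints that excludes them.

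**Cost.** Footnotes, a change to record selection and one added sensitivity analysis; no new data. A few CDAI and hs-CRP values become missing at Week 4 and count as failures for binary endpoints. In the calprotectin sensitivity analysis of change from baseline, the excluded subjects drop out, since LOCF has no earlier post-baseline value to carry.

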During the OL period, in addition to the TB screening described above, laboratory tests (hematologic and chemical analysis, including hs-CRP) will be performed during study visits at Weeks 12, 16, 20, and 26/Premature Discontinuation, and urinalysis will be performed at Weeks 12, 20, and 26/Premature Discontinuation.

AEs will be collected during the study and for 70 days after the last study drug administration.

Crohn's Disease Activity Index (CDAI) will be obtained during the Screening Period and at Weeks 0, 2, 4, 6, 8, 12, 16, 20, and 26/Premature Discontinuation. If the subject doses onsite then the CDAI will also be completed at Weeks 10, 14, 18, 22, and 24. The inflammatory bowel disease questionnaire (IDBQ) will be administered at Weeks 0, 4, 8, and 26/PD.

Subjects should adhere to the required visit schedule. Study visits should occur within the ± 3 day visit window. The Baseline visit at Week 0 should occur within 35 days of the Screening visit.

Diagnosis and Main Criteria for Inclusion/Exclusion:

Main Inclusion:

1. Male or female of Chinese descent with full Chinese parentage 18 to 70 years (inclusive) of age at Baseline (Week 0).
2. Confirmed diagnosis of Crohn's disease for at least 3 months prior to Baseline (Week 0). Appropriate documentation of biopsy results consistent with the diagnosis of CD, in the assessment of the Investigator, must be available.
3. Subject has hs-CRP ≥ 3 mg/L in all laboratory measurements during the Screening Period.
4. Crohn's Disease Activity Index (CDAI) ≥ 220 and ≤ 450 at Baseline (Week 0) despite concurrent or prior treatment with an adequate course, in the opinion of the investigator, of at least one of the following (oral corticosteroids or immunosuppressants or both as defined below):
 - Subjects taking oral corticosteroids, excluding budesonide:
 - Oral corticosteroid dose must be ≤ 20 mg/day (prednisone or equivalent);
 - For subjects with a dose > 10 and ≤ 20 mg/day, dose has been stable for at least 7 days prior to Baseline and the duration of the current steroid course has been at least 14 days prior to Baseline.
 - For subjects with a dose ≤ 10 mg/day, dose has been stable for at least 10 days prior to Baseline (Week 0) and the duration of the current steroid course has been at least 14 days prior to Baseline (Week 0).
 - Subjects taking oral budesonide:
 - Dose must not exceed 9 mg/day;

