5.4 Removal of Subjects from Therapy or Assessment

5.4.1 Discontinuation of Individual Subjects

A subject may withdraw from the study at any time. The Investigator may discontinue any subject's participation for any reason, including an adverse event, safety concerns or failure to comply with the protocol.

Subjects will be withdrawn from the study immediately if any one of the following occurs:

- Clinically significant abnormal laboratory result(s) or adverse event(s), as determined by the Investigator in consultation with the AbbVie SDP.
- The Investigator believes it is in the best interest of the subject.
- The subject requests withdrawal from the study.

- Inclusion and exclusion criteria violation was noted after the subject started study drug, when continuation of the study would place the subject at risk as determined by the AbbVie SDP (see Section 5.2 and Section 7.0).
- Introduction of prohibited medications or dosages when continuation of the study drug would place the subject at risk as determined by the AbbVie SDP.
- Subject is non-compliant with TB prophylaxis.
- Subjects with negative TB Screening before Week 0 who later develop a positive/indeterminate QuantiFERON-TB Gold In-Tube test result or CXR/chest CT findings.
- The subject becomes pregnant while on study drug.
- Subject has dysplasia or a malignancy, except for localized non-melanoma skin cancer. Discontinuation for carcinoma in-situ of the cervix is at the discretion of the Investigator.
- Subject is diagnosed with lupus-like syndrome, multiple sclerosis or demyelinating disease.
- Subject is significantly non-compliant with study procedures which would put the subject at risk for continued participation in the trial, as determined by the Investigator, in consultation with the AbbVie SDP.

If, during the course of study drug administration, the subject prematurely discontinues study drug use, the procedures outlined for the Premature Discontinuation Visit must be completed within 2 weeks of the last dose of study drug, and preferably prior to the initiation of another therapy. However, these procedures should not interfere with the initiation of any new treatments or therapeutic modalities that the Investigator feels are necessary to treat the subject's condition. Following discontinuation of the study drug, the subject will be treated in accordance with the Investigator's best clinical judgment.

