Week 22	155	149 – 162
Week 24	169	163 – 176
Week 26	183	177 – 190

Rx Day B = date of visit – date of first dose of adalimumab + 1

- a. Date of first dose of adalimumab in double-blind treatment period.

Table 7. Visit Windows for Analysis of hs-CRP, Chemistry and Hematology (Any Adalimumab)

Visit Week	Nominal Day	Time Window (Rx Day B Range)
Week 0	1 ^a	≤ 1
Week 2	15	2 – 22
Week 4	29	23 – 36
Week 6	43	37 – 50
Week 8	57	51 – 71
Week 12	85	72 – 99
Week 16	113	100 – 127
Week 20	141	128 – 162
Week 26	183	163 – 190

Rx Day B = date of visit – date of first dose of adalimumab + 1

a. Date of first dose of adalimumab in double-blind treatment period.

Table 8. Visit Windows for Analysis of Urinalysis (Any Adalimumab)

Visit Week	Nominal Day	Time Window (Rx Day B Range)
Week 0	1 ^a	≤ 1
Week 4	29	2 – 43
Week 8	57	44 – 71
Week 12	85	72 – 112
Week 20	141	113 – 161
Week 26	183	162 – 190

Rx Day B = date of visit – date of first dose of adalimumab + 1

a. Date of first dose of adalimumab in double-blind treatment period.

Table 9. Visit Windows for Analysis of Fecal Calprotectin and IBDQ (Any Adalimumab)

Visit Week	Nominal Day	Time Window (Rx Day B Range)
Week 0	1 ^a	≤ 1
Week 4	29	2 – 43
Week 8	57	44 – 71
Week 26	183	72 – 190

Rx Day B = date of visit – date of first dose of adalimumab + 1

a. Date of first dose of adalimumab in double-blind treatment period.

Definition of Missing Data Imputation

The following imputation methods will be used to impute missing values in the efficacy analyses. In addition, an observed case analysis will be performed.

Non-Responder Imputation (NRI)

The NRI approach is used for binary efficacy variables. These variables can take values of 'Achieved' or 'Not Achieved' or may be missing for any reason including discontinuation from study. According to the NRI imputation approach, all missing value will be considered as 'Not Achieved.'

Subjects who dose-escalate from OL adalimumab 40 mg eow to OL adalimumab 80 mg eow due to disease flare or non-response will be imputed as 'Not Achieved' in the analysis of binary efficacy variables.

For the analysis of Week 26 efficacy variables only for dose-escalated subjects, the remission/response status will be determined based on the observed data at Week 26 after the dose escalation.

Last Observation Carried Forward (LOCF)

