10.3 Secondary Efficacy Analyses

The Week 26 efficacy endpoint is proportion of subjects who achieve clinical remission at Week 26 (CDAI < 150) in subjects who achieved clinical response (decrease in CDAI ≥ 70 points from Baseline) at Week 8. The one sample Exact test will be performed by comparing it to the clinically meaningful remission rate of 30%, and the two-sided 95% CI will be provided.

Key secondary efficacy endpoints include:

- Proportion of subjects who achieve CDAI < 150 plus a reduction in hs-CRP of at least 50% from Baseline at Week 4.
- Proportion of subjects who achieve CDAI < 150 plus a reduction in hs-CRP of at least 50% from Baseline at Week 26 in subjects who achieved decrease in

CDAI \geq 70 points from Baseline plus at least 30% reduction in hs-CRP from Baseline at Week 8.

- Proportion of subjects who discontinue corticosteroid use and achieve clinical remission (CDAI $<$ 150) at Week 26 in subjects who were taking steroids at Baseline and who achieved clinical response (decrease in CDAI \geq 70 points from Baseline) at Week 8.
- Proportion of subjects who discontinue corticosteroid use and achieve CDAI $<$ 150 plus a reduction in hs-CRP of at least 50% from Baseline at Week 26 in subjects who were taking steroids at Baseline and who achieved decrease in CDAI \geq 70 points from Baseline plus a reduction in hs-CRP of at least 30% from Baseline at Week 8.
- Proportion of subjects who achieve clinical response (decrease in CDAI \geq 70 points from Baseline) at Week 4.
- Proportion of subjects who achieve decrease in CDAI \geq 70 points from Baseline plus a reduction in hs-CRP of at least 30% from Baseline at Week 4.
- Proportion of subjects who achieve CDAI $<$ 150 and hs-CRP $<$ 3 mg/L at Week 4.
- Proportion of subjects who achieve CDAI $<$ 150, hs-CRP $<$ 3 mg/L at Week 26 in subjects who achieved clinical response (decrease in CDAI \geq 70 points from Baseline) at Week 8.
- Proportion of subjects who achieve IBDQ remission (IBDQ \geq 170 points) at Week 4.
- Proportion of subjects who achieve IBDQ remission at Week 26 in subjects with clinical response (decrease in CDAI \geq 70 points from Baseline) at Week 8.
- Change from Baseline in fecal calprotectin level at Week 4.
- Proportion of subjects who achieve CDAI $<$ 150, hs-CRP $<$ 3 mg/L and fecal calprotectin $<$ 250 μ g/g at Week 4.

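### SAP Table 5 counts an IBDQ from a premature discontinuation visit as Week 26 from about Day 58, so early leavers can be scored as Week 26 IBDQ remitters under NRI

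*SAP*

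**What the plan says.** - **Visit mapping.** SAP 6.0 (Definition of Analysis Windows) states that "the following rules will be applied to assign actual visits to protocol-specified visits including early termination visits", and that "windows will not discard any post-baseline measurement recorded on the CRF".
- **IBDQ window.** Table 5 has no IBDQ visit between Week 8 and Week 26. Footnote c opens the last window: "For Week 26 OL, visit window was from Rx Day 72 or the date of the first injection in OL period + 1" (if there was one), whichever is earlier. It closes on Day 190.
- **Collection at exit.** The Protocol synopsis says the "questionnaire (IDBQ) will be administered at Weeks 0, 4, 8, and 26/PD". Protocol 5.4.1 adds that the "procedures outlined for the Premature Discontinuation Visit must be completed within 2 weeks of the last dose of study drug".
- **Endpoint.** One of the 13 key secondary endpoints in SAP 10.3 is "Proportion of subjects who achieve IBDQ remission at Week 26 in subjects with clinical response" at Week 8. The remission cut-off is 170 points.
- **Missing data.** SAP 6.0 says binary variables "may be missing for any reason including discontinuation from study". It continues: "According to the NRI imputation approach, all missing value will be considered as" not achieved. Dose-escalated subjects are also set to not achieved. SAP 10.3 applies NRI where data are missing at the time point evaluated, with LOCF as sensitivity analysis; SAP 6.0 adds an observed case analysis.

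**The concern.** NRI is meant to count a subject who does not reach the time point as a failure. Table 5 prevents this for IBDQ. A result taken at exit, up to four months before Week 26, is labelled Week 26, so nothing is missing and nothing is imputed. For these subjects NRI in effect becomes LOCF, the method that the SAP reserves for sensitivity analysis.

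The same subject then gets opposite Week 26 results on two maintenance endpoints: failure on CDAI remission and success on IBDQ remission, from one visit. The IBDQ endpoint is a single-arm rate in Week 8 responders, so no control arm offsets the inflation.

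Leaving while well is possible by design. Subjects not on TB prophylaxis who become QuantiFERON-positive after a negative screening test are withdrawn (Protocol 5.3.1.1, TB Screening), as are subjects who become pregnant (Protocol 5.4.1).

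**Working it through.** **The plan's own figures.** The SAP gives no power or reference rate for Week 26 IBDQ remission. The nearest stated figure is power of at least 99% for Week 26 CDAI remission (52% against 30%, n = 100, exact test, two-sided 0.05; SAP 4.3). It reproduces: the smallest count whose upper-tail probability under 30% is at most 0.025 is 40 (0.0210), and the power at 52% is 0.9939. Only the denominator of about 100 Week 8 responders is used below.

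**Days.** Visit day = 7 × week + 1, so Week 8 = 57, Week 22 = 155, Week 24 = 169 and Week 26 = 183.

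- Table 5 window start = the earlier of 72 and 57 + 1, that is Day 58. With the ±3-day visit tolerance it is Day 55 to 61. Without an open-label injection it is Day 72.
- Earliest Week 26 value: 183 − 58 = 125 days before nominal.
- Latest discontinuation visit = last dose + 14 days: Day 71 after a Week 8 dose, Day 169 after Week 22, Day 183 after Week 24.

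A subject whose last dose is at Week 8 to Week 22 is therefore seen by Day 169, before the CDAI Week 26 window opens on Day 177 (Table 2). A subject whose last dose is at Week 24 may be seen on Day 170 to 176, also before it.

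**Window widths for Week 26.**

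| Measure | Days | Width |
|---|---|---|
| IBDQ (Table 5) | 58–190 | 133 |
| Urinalysis (Table 4) | 162–190 | 29 |
| hs-CRP (Table 3) | 163–190 | 28 |
| CDAI (Table 2) | 177–190 | 14 |

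**Effect on the rate.** Let C completers include R remitters, and let d dropouts with an exit IBDQ before Day 177 include a with IBDQ of at least 170. Assume no dose escalation and C + d = 100.

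- NRI: (R + a)/100 as written, R/100 if exit values are not Week 26. The difference is a points and is never negative.
- Observed case: (R + a)/(C + d) as written, R/C otherwise. The current rule raises it only if a/d > R/C.

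Worked case (assumed: C = 90, R = 35, d = 10, a = 3), with Clopper-Pearson 95% intervals:

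| Analysis | As written | After the fix |
|---|---|---|
| NRI | 38/100 (28.5–48.3%) | 35/100 (25.7–45.2%) |
| LOCF | 38/100 | 38/100 |
| Observed case | 38/100 | 35/90 = 38.9% (28.8–49.7%) |

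As written, all three analyses coincide. The rule raises NRI by 3.0 points and lowers observed case by 0.9. With a = 5, NRI rises by 5.0 points, and observed case is 40/100 against 38.9%, a rise of 1.1.

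**Range.** Assumed: 5–15% non-escalated dropouts, of whom 10–40% have IBDQ of at least 170. Then 0.05 × 0.10 = 0.5 points and 0.15 × 0.40 = 6 points.

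**The case against.** - **The NRI text names discontinuation as a reason for missingness, so a discontinued subject could be read as missing.** That sentence lists a possible cause. It does not make a value missing when one falls in the window, and no other text does. The mapping rule expressly covers early termination visits.
- **Windowing exit visits is a uniform convention, and a wide window is natural when no IBDQ is scheduled between Weeks 8 and 26.** Both points are true. Table 3 also maps an hs-CRP exit visit on Day 163–176 to Week 26, and the hs-CRP and urinalysis windows are narrower because a Week 20 sample exists. The fault is not the width but the placing of discontinuation visits in it.
- **The stakes are modest.** This stands. The primary endpoint and Week 26 CDAI remission are untouched. So is the Week 26 calprotectin composite under NRI, because its CDAI component is missing. There is no IBDQ reference rate and no multiplicity hierarchy (SAP 10.4), so no stated test is at risk.
- **The size is assumed, and many leavers will be unwell.** This also stands. Withdrawals for inadequate response or adverse events seem less likely to have a high IBDQ, and the top of the range pairs both upper assumptions. A 3-point shift is about a third of the exact interval's half-width of roughly 10 points. QuantiFERON withdrawal shows that the route exists, not how often it is taken.
- **A cut at Day 177 is abrupt.** A subject who leaves on Day 170–176 after the Week 24 dose becomes a failure, while a completer seen equally early does not. This is a real but small cost, and Day 177 is the boundary that the SAP already uses for CDAI.

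**Conclusion.** The rule is wrong as written. It follows from explicit text that a non-escalated Week 8 responder with an exit IBDQ of at least 170 before Day 177 is counted as a Week 26 remitter. Under NRI the effect can only raise the rate, by 1 point per such subject if there are about 100 Week 8 responders. The total cannot be known from the documents; 0.5 to 6 points rests wholly on the assumed dropout and exit-remission ranges. It also requires that an IBDQ is recorded at the exit visit; if none is, NRI works as intended.

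The harm is to the reported rate and confidence interval of one key secondary endpoint. The planned sensitivity analyses do not expose it. The point should be corrected, but it does not threaten the trial's main conclusions.

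**What to change.** Add to SAP 6.0 and Table 5, as an explicit exception to the early-termination mapping rule: an IBDQ or calprotectin result from a premature discontinuation visit that Table 5 would place in Week 26, but which falls before Day 177, is labelled early termination and is not a Week 26 value.

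- **Handling.** For IBDQ remission, Week 26 is then missing: not achieved under NRI, excluded from observed case, and carried forward only in LOCF. The results stay in listings, so nothing is discarded.
- **Basis.** Use discontinuation status, which the disposition tables (SAP 8.0) already need. A completer's final visit stays Week 26 even if early, for example on Day 172.
- **Unchanged.** The Week 4 and Week 8 windows stay. Discontinuation visits on Day 177–190 still count as Week 26, as they do for CDAI. Table 9 also stays: it counts from the first adalimumab dose, so a placebo-arm completer's Week 26 visit falls near Day 183 − 28 = 155 (152–158), and a Day 177 cut there would be wrong.

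The cost is one sentence and one programming condition before database lock, with no new data. The NRI rate may be lower, and observed case may move either way. Two small inconsistencies remain: a completer with an early final visit has a Week 26 IBDQ while that visit's CDAI maps to Week 24, and an early exit calprotectin result may still be labelled Week 26 in the Any Adalimumab summaries under Table 9.
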